Sponsor	University Hospital Southampton NHS Foundation Trust
Trial Centres	Southampton - NIHR Clinical Research Facility, Southampton University Hospital NHS Foundation Trust, [name]
Sponsor Study Reference	RHM MED1776
Design	Open label, single-centre, first-in-human, adaptive dose escalation Phase I COVID-19 DNA vaccine trial.
Clinical Phase	
Population	Healthy, males and non-pregnant females aged 18-50 years who are immunised no less than 12 weeks prior with 2 doses of SARS-CoV-2 vaccine and have no history of serological evidence of prior SARS- CoV-2 infection (seronegative for N)
Sample size	Total: 36 volunteers
	Stage 1
	Group 1: 6 volunteers; 2 doses of pEVAC-PS at 0.2mg (lowest dose)
	Intradermally
	Stage 2 subject to safety and immunogenicity analysis from stage 1 after 4w post 2 nd dose
	Primary immunogenicity target met Expanded group 1: 12 volunteers; 2 doses of pEVAC-PS at 0.2mg intradermally
	Review for plan of reduced dose formulation and testing if continued safety and immunogenicity targets met in expanded group
	Primary immunogenicity target not met
	Group 2a: 9 volunteers; 2 doses of pEVAC-PS at 0.4mg intradermally PLUS
	Group 2b: 9 volunteers; 2 doses of pEVAC-PS at 0.8mg intradermally
	Very Poor/No response
	Group 2a: 9 volunteers; 2 doses of pEVAC-PS at 0.8mg intradermally PLUS
	Group 2b: 9 volunteers; 2 doses of pEVAC-PS at 1.2mg intradermally
	Stage 3 subject to safety and immunogenicity analysis from stage 2 after 4w post 2 nd dose

	Primary immunogenicity target met
	Group 3: 12 volunteers, 2 doses of pEVAC-PS at the dose with the
	best immunogenicity and reactogenicity profile from Groups 2a or 2b
	Primary immunogenicity target not met at 2x 0.8mg ID
	Group 2c: 12 volunteers; 2 doses of pEVAC-PS at 1.2mg intradermally
Follow up	COVID-19 vaccinated volunteers (immunised no less than 12 weeks
duration	prior to enrolment), and who have no prior history or serological
	evidence of SARS-CoV-2 infection will be followed up for a total of
	approximately 6 months from the time of receiving the first dose of
	pEVAC-PS (this is an estimate and may vary in accordance with the
	specified time windows for each attendance).
Planned Trial	18 months (this includes up to 6 months during the recruitment and
Period	dosing phase with a follow-up period of up to 12 months).
Primary Objective	To assess the safety and reactogenicity of a new pan-Sarbeco
	Coronavirus DNA candidate vaccine pEVAC-PS in a boosting regime
	in healthy volunteers.
Secondary	To assess the humoral immunogenicity of pEVAC-PS when
Objectives	administered to healthy volunteers, through the analysis of SARS-CoV
	and SARS-CoV-2 RBD antibody titres
	Assess optimum dosing of candidate vaccine pEVAC-PS
	To assess long term (up to 12 months) humoral immunogenicity of
	the candidate vaccine pEVAC-PS administered by the needle-free
	technology (PharmaJet)
Investigational	
Broduct	pEVAC-PS
	1:
rorm	Liquia
Dose	pEVAC-PS; 1.2mg ID, 0.8mg ID, 0.4mg ID, 0.2mg ID
Route	Intradermal (ID) administration into the deltoid region of the arm (split
	left and right with >0.2mg)

Abbreviations

AE	Adverse Event					
AR	Adverse Reaction					
ALS	Advanced life support					
AUC	Area Under the Curve					
CI	Chief Investigator					
CBF	Clinical Bio-manufacturing Facility					
COVID-19	Coronavirus Disease 2019					
CRF	Case Report File					
CTRG	Clinical Trials Research Governance					
DSUR	Development Safety Update Report					
EPSC	Early Phase Safety Committee					
ELISA	Enzyme-linked immunosorbent assay					
ELISPOT	Enzyme-linked immunospot					
FIH	First in Human					
FBC	Full blood count					
GCP	Good Clinical Practice					
GMP	Good Manufacturing Practice					
GP	General Practitioner					
НВ	Haemoglobin					
HBsAg	Hepatitis B Surface Antigen					
HCV	Hepatitis C Virus					
HIV	Human Immunodeficiency Virus					
HPA	Health Protection Agency					
HRA	Health Research Authority					
IB	Investigators Brochure					
ICH	International Conference on Harmonisation					
ICU	Intensive Care Unit					
IDT	Indefinite Delivery type					
ILS	Immediate Life Support					
IMI	Innovative Medicines Initiative					
IMP	Investigational Medicinal Product					
IMPD	Investigational Medicinal Product Dossier					
ISF	Investigator Site File					

LSC	Local safety committee					
LSM	Local safety monitor					
MHRA	Medicines and Healthcare Products Regulatory Agency					
NHS	National Health Service					
NIH	National Institute of Health (USA)					
NIHR-CRF	National Institute for Health Research Clinical Research Facility					
PBMC	Peripheral blood mononuclear cells					
PCR	Polymerase Chain Reaction					
LVZ	Laboratory of Viral Zoonotics					
PI	Principal Investigator					
QA	Quality Assurance					
QC	Quality Control					
QP	Qualified Person					
REC	Research Ethics Committee					
SAB	Scientific Advisory Board					
SAE	Serious Adverse Event					
SAR	Serious Adverse Reaction					
SARS-CoV or	Severe Acute Respiratory Syndrome Coronavirus					
SARS-CoV-1						
SARS-CoV-2	Severe Acute Respiratory Syndrome Coronavirus 2					
SDV	Source Data Verification					
SOP	Standard Operating Procedure					
SUSAR	Suspected Unexpected Serious Adverse Reaction					
TOPS	The Over-volunteering Prevention System					
UAR	Unexpected Adverse Reaction					
UHS NHS FT	University Hospital Southampton NHS Foundation Trust					
ULN	Upper limit of normal					
UK	United Kingdom					
VIS	Volunteer Information Sheet					
WBC	White blood cells					
WHO	World Health Organisation					

1. Background & Rationale

1.1 Background

A number of SARS-CoV-2 viruses have been designated as Variants of Concern (VOC) by the WHO because of changes in the spike protein which may contribute to future vaccine escape. Furthermore, there is the constant threat of new and re-emerging (i.e. SARS or SARS-related) Sarbeco (ACE2 using) Coronaviruses.

Since 1966 there have been 7 documented animal to human spillovers of Coronaviruses, 3 of which have caused High Consequence Infectious Diseases in Humans. SARS-CoV caused international epidemics in 2002/2003, and SARS-CoV-2 is the cause of the current global COVID-19 pandemic. These highly contagious, respiratory transmitted ACE-2 receptor using Sarbeco Coronaviruses belong to a larger group of Beta-Coronaviruses naturally carried in bats, representing current and future threats. The global human COVID-19 pandemic is now witnessing the evolution of a great number of variants of SARS-CoV-2.

Vaccines that protect against SARS-CoV-2 and related Sarbeco-Coronaviruses have been developed using Digital Immune Optimised Synthetic Vaccine (DIOSynVax) technology developed in Cambridge. This broadly protective approach is needed for Coronaviruses such as SARS-CoV-2 and the SARS ACE2 receptor using Sarbeco Coronaviruses that have the potential to spill-over to humans from their animal reservoirs.

For the DIOS pan-Sarbeco vaccine candidate (pEVAC-PS), we have designed an antigen to induce immune responses against the Sarbeco Coronaviruses in order to protect against SARS-CoV-2, SARS-CoV and future outbreaks of related Coronaviruses. The majority of first wave SARS-CoV-2 vaccines in clinical trials and deployment are Spike (S) -based vaccines. There are two major concerns about single antigen S-based vaccine approaches due to the number of new circulating variants of concern (VOC); reduced vaccine efficacy, and the development of vaccine resistant strains.

The approach to design a pan-Sarbeco Coronavirus vaccine included structure-informed, computationally generated antigen libraries that were screened, selecting those conserved sub structures that elicit potent, specifically-targeted effector immune responses. High throughput screens, *in vivo* pre-clinical immune selection and vaccine efficacy readouts, which were down-selected to pEVAC-PS, an optimised-RBD vaccine capable of neutralising SARS-CoV-2 (2019), SARS-CoV-1 (2003), and other bat Sarbeco Coronaviruses.

DNA offers several potential advantages in that DNA vaccines are thermostable, are relatively straight-forward to manufacture and can be delivered using a needle-free device.

1.2. Study Rationale

Vaccines that protect against multiple related viruses have been developed using DIOSynVax technology. This broadly protective approach is needed for Coronaviruses such as SARS-CoV-2 and SARS-CoV, two of numerous related viruses that have the potential to cause future outbreaks from zoonotic reservoirs. The pEVAC-PS vaccine was designed to induce highly focussed immune responses against key neutralising antibody targets of the Sarbeco Coronaviruses in order to protect against SARS-CoV-2, SARS-CoV and potential future outbreaks of related Coronaviruses. pEVAC-PS is well-positioned to boost existing, licenced SARS-CoV-2 vaccines and to induce SARS-CoV antibody responses.

DNA sequences encoding the antigens are optimised for expression in mammalian cells before inserting into our DNA plasmid expression vector pEVAC. This vector is a flexible vaccine platform and any combination of antigens can be inserted to produce a different vaccine. DIOSynVax antigen inserts are engineered to be readily transferable to other scaleable vaccine delivery systems, such as Adenoviral or mRNA vectors.

This study will use an established needleless vaccine delivery technology to assess the optimal dose required to trigger patients' cells to produce the antigens, be recognised by participants immune systems and boost antibody titres that will induce durable protection against SARS-CoV-2 and SARS-CoV. Combined with needleless and powerless (no electrical source required) delivery, this platform offers a safe, widely deployable pan-Sarbeco Coronavirus vaccine for large scale immunisation programmes.

1.3 pEVAC-PS Vaccine

1.4 Pre-clinical studies of pEVAC-PS

1.5. Dose Rationale

The CE-marked PharmaJet Tropis intradermal (ID) delivery of DNA has demonstrated to be highly effective at reducing the dose required for anti-viral responses in several different systems. An adaptive dose escalation regime follows to discover the lowest dose of DNA which will produce an effective immune response when delivered intradermally, with potential doses of 1.2mg, 0.8mg, 0.4mg and 0.2mg.

Objective	Outcome measure			
Primary To assess the safety and reactogenicity of a new pan-Sarbeco Coronavirus DNA candidate vaccine pEVAC-PS in a boosting regime in healthy volunteers.	 a) Occurrence of solicited local reactogenicity signs and symptoms for 7 days following vaccination; b) Occurrence of solicited systemic reactogenicity signs and symptoms for 7 days following vaccination; c) Occurrence of unsolicited adverse events (AEs) for 28 days following vaccination; d) Change from baseline for safety laboratory measures and; e) Occurrence of disease enhancement episodes 			
Secondary To assess the humoral immunogenicity of pEVAC-PS when administered to healthy volunteers as a booster vaccine, through the analysis of SARS-CoV and SARS-CoV-2 RBD antibody titres. To assess the humoral immunogenicity of the candidate vaccine pEVAC-PS at 28 days (4 weeks) after 2 doses of pEVAC-PS have been administered 28 days apart, given by needle-free technology (PharmaJet); both administered in split doses, left and right deltoids (when >0.2mg)	 a) Serology: receptor binding domain (RBD) responses in the majority of vaccinees per group for SARS-CoV and SARS-CoV-2 			
Secondary Assess optimum dosing of candidate vaccine pEVAC-PS	a) Compare dose tolerability and results of immunogenicity of up to four different doses of PharmaJet ID			

2. Objectives and Endpoints

	administration at 28 days (4 weeks)
	after the second dose of vaccine
Secondary	a) Serology: receptor binding domain
To assess long term (up to 12 months)	(RBD) for SARS-CoV and SARS-
humoral immunogenicity of the candidate	CoV-2 RBD pre and post-
vaccine pEVAC-PS administered by the	immunisation.
needle-free technology (PharmaJet)	
administered as 2 doses (split L&R	
when >0.2mg)	

3. Study Design

3.1. Study Design Overview

This is an adaptive, open label phase I dose escalation study of the safety, tolerability, immunogenicity and intra-dermal administration dose finding for the pEVAC-PS vaccine candidate against SARS-CoV and SARS-CoV-2. This study will recruit up to 36 healthy volunteers in up to 3 stages. All volunteers recruited will be healthy, male or non-pregnant female adults aged between 18 and 50 years who have been vaccinated no less than 12 weeks prior with 2 doses of a SARS-CoV-2 vaccine and have no history of infection and are seronegative for N.

The sentinel participant in each group will be observed for 1hr post vaccination and contacted 24hrs afterwards by the medical team to review symptoms and check against symptom diary. If no safety concerns are identified (section 7.9.1), the subsequent 5 participants can be vaccinated a minimum of 1 hour apart. Each participant will be observed for 60 minutes post vaccination. After review of participants in group 2a at 72hrs post dosing with the second immunisation, if no stopping criteria have been met (section 7.9) then the sentinel participant at the next dose level in 2b can be vaccinated.

Figure 1 (page 19) shows our approach to dose escalation to maximise participant numbers in groups that may inform future large scale clinical trials.

Stage 1

Group 1 will consist of 6 volunteers receiving 2 administrations of the lowest dose of ID injection at 0.2mg. There will be a review of the immunogenicity data 4 weeks following the second administration prior to proceeding to stage 2.

Stage 2

Group and dose allocation in stage 2 will depend on the results of the safety and immunogenicity analysis in stage 1, according to pre specified target immunogenicity outcomes.

a) Primary immunogenicity target met

Group 1 will be expanded with an additional 12 participants receiving 2 administrations of 0.2mg ID. If no safety issues are noted during expansion group and immunogenicity targets continue to be met, the study will be halted and a further review will be conducted by the study team to determine a reduced dose formulation and study regime, which will follow as a planned amendment to this protocol.

b) Primary immunogenicity target not met

2 additional groups consisting of 9 participants will be enrolled. Group 2a will receive 2 administrations of 0.4mg ID, and group 2b will receive 2 administrations of 0.8mg ID.

c) Very Poor/ No response

2 additional groups consisting of 9 participants will be enrolled. Group 2a will receive 2 administrations of 0.8mg ID, and group 2b will receive 2 administrations of 1.2mg ID.

There will be a review conducted of the safety and immunogenicity data 4 weeks after the second administration of vaccine for groups 2a and 2b to determine how to proceed in Stage 3.

Stage 3

If primary immunogenicity target is met during stage 2, then the group with the optimum immunogenicity and reactogenicity profile from Groups 2a or 2b will be expanded with an additional 12 participants in Group 3.

If the target is not met from group 2a or 2b (0.8mg), then an additional 12 participants will be enrolled into group 2c, who will receive 2 administrations of 1.2mg ID.

3.1.1. Immunogenicity endpoints

The adaptive protocol is based on reviews of immunogenicity data which will be made 4 weeks following the second administration of pEVAC-PS (8 weeks following the first dose). The decision for how to proceed will be made on the basis of the proportion of participants within each group who have seroconverted. Seroconversion will be defined as a positive readout from the SARS-CoV and/or SARS-CoV-2 RBD ELISA. The dose used for each group will be classified as either having met immunogenicity target, failed to meet immunogenicity target, or had very poor / no response. Proportions of participant seroconversion will be classed as the following:

Stage 1 – Meets immunogenicity target if 5 or 6 out of 6 participants have at least a 2-fold increase in Ab titre (at 0.2mg) we proceed to Expanded Group 1.

- Stage 2 (Expanded Group 1) if 12/12 participants have a 2-fold increase in Ab titre (at 0.2mg) consider to re-formulate and reduce the dose for a new study.
- Stage 2 (Expanded Group 1) if 10 or more of the 12 participants have at least a 2-fold increase in Ab titre (at 0.2mg) we select 0.2mg as the optimum dose to move forward into a Phase II study.
- Stage 2 (Expanded Group 1) if <=9 participants have a 2-fold increase in Ab titre (at 0.2mg) then a further 9 participants will be recruited to group 2a (0.4) and 2b (0.8mg) each, to be run in parallel.

 - The study will conclude after running groups 2a and 2b.

Stage 1 – Fails to meet immunogenicity target if only 3 or 4 out of 6 participants have at least a 2-fold increase in Ab titre, then we proceed to Groups 2a (0.4mg) and 2b (0.8mg) in parallel.

- Stage 2 if 7-9 or more participants have a 2-fold increase in Ab titre (at 0.4 or 0.8 mg) we expand whichever group has the higher number of responders. If both groups 2a and 2b have 9 responders, we will expand the lower dose.
- Stage 2 if <7 participants have a 2-fold increase in Ab titre (at 0.4 or 0.8 mg) we move to Stage 3 and increase dose to 1.2mg.

Stage 1 – With a poor response, if 2 or less participants out of 6 have a 2-fold increase in Ab titre, we proceed to Groups 2a (0.8mg) and 2b (1.2mg) in parallel.

- Stage 2 if 7-9 participants have a 2-fold increase in Ab titre (at 0.8 or 1.2mg) we expand whichever group has the higher number of responders.
- Stage 2 if <7 participants have a 2-fold increase in Ab titre at 0.8mg and 1.2mg the trial will conclude.

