4.1. Inclusion Criteria

The healthy adult volunteers must meet all the following inclusion criteria to be eligible for the study:

- Healthy adults aged 18-50 years.
- Able and willing (in the Investigator's opinion) to comply with all study requirements (participants must not rely on public transport or taxis).
- Willing to allow the investigators to discuss the volunteer's medical history with their General Practitioner and access all medical records when relevant to study procedures.

- Agreement to refrain from blood donation during the course of the study.
- Provide written informed consent.
- Completed a 2 dose primary immunisation course against COVID-19, with the most recent dose administered no less than 12 weeks (84 days) previously

Female volunteers of childbearing potential are required to use an effective form of contraception at enrolment and until after 3 months following their last personal dose of vaccination within the study. A woman of childbearing potential is defined as a premenopausal female who is capable of becoming pregnant. Menopause can be diagnosed in a woman aged over 50 after one year of amenorrhoea (this applies only if the woman is not using hormonal contraception).

Acceptable forms of contraception for female volunteers are as follows:

- Established use of oral, injected or implanted hormonal methods of contraception
- Placement of an intrauterine device or intrauterine system
- Total abdominal hysterectomy or surgical sterilisation
- Barrier methods of contraception (condom or occlusive cap with spermicide)
- Male sterilisation if the vasectomised partner is the sole partner for the subject
- True abstinence when this is in line with the preferred and usual lifestyle of the subject

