4.2 Exclusion criteria

The volunteer may not enter the study if any of the following apply:

- History of laboratory confirmed MERS, SARS-CoV-1 or SARS-CoV-2 infection
- Seropositive for SARS-CoV-2 Nucleocapsid IgG at screening
- Have an anti-SARS-CoV-2 and a SARS-CoV-1 RBD response of more than 2 AUC (Area Under the Curve) units
- Planned receipt of any vaccine other than the study intervention within 30 days before and after each study vaccination.
- Administration of immunoglobulins and/or any blood products within the three months preceding the planned administration of the vaccine candidate.
- Any confirmed or suspected immunosuppressive or immunodeficient state, including HIV infection; asplenia; recurrent severe infections and use of immunosuppressant medication within the past 6 months, except topical steroids or short-term oral steroids (course lasting <14 days).
- Any autoimmune conditions, except mild psoriasis, well-controlled autoimmune thyroid disease, vitiligo or stable coeliac disease not requiring immunosuppressive or immunomodulatory therapy.
- History of allergic disease or reactions likely to be exacerbated by any component of the pEVAC-PS vaccine
- Any history of angioedema.
- Any history of anaphylaxis.
- Pregnancy, lactation or willingness/intention to become pregnant for 3 months following the last personal dose of vaccine in this trial.

- History of cancer (except basal cell carcinoma of the skin and cervical carcinoma in situ).
- History of serious psychiatric condition likely to affect participation in the study (e.g. ongoing severe depression, history of admission to an in-patient psychiatric facility, recent suicidal ideation, history of suicide attempt, bipolar disorder, personality disorder, alcohol and drug dependency, severe eating disorder, psychosis, use of mood stabilisers or antipsychotic medication).
- Bleeding disorder (e.g. factor deficiency, coagulopathy or platelet disorder), or prior history of significant bleeding or bruising following IM injections or venepuncture.
- Any other serious chronic illness requiring hospital specialist supervision.
- Chronic respiratory diseases, including mild asthma (resolved childhood asthma is allowed)
- Chronic cardiovascular disease (including hypertension), gastrointestinal disease, liver disease (except Gilberts Syndrome), renal disease, endocrine disorder (including diabetes) and neurological illness (excluding migraine)

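### Section 3.1.1 gives two different responder definitions for the count that drives every adaptation, and its and/or antigen wording lets a SARS-CoV-2-only boost meet the target

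*Protocol*

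**What the plan says.** Protocol Section 3.1.1 sets the basis for adaptation: "The decision for how to proceed will be made on the basis of the proportion of participants within each group who have seroconverted". It then defines the term: "Seroconversion will be defined as a positive readout from the SARS-CoV and/or SARS-CoV-2 RBD ELISA". No baseline condition is attached.

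The same section goes on to class the seroconversion proportions by a different measure. For Stage 1: "Meets immunogenicity target if 5 or 6 out of 6 participants have at least a 2-fold increase in Ab titre". The later branches (10 or more of 12, 12 of 12, 7 to 9 of 9, fewer than 7 of 9) also count participants with a 2-fold increase. None names the antigen or the visit against which the increase is measured. The review itself is timed at 4 weeks after the second administration.

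Three other places bear on this:

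- The objectives table in Section 2 gives the humoral secondary outcome as RBD "responses in the majority of vaccinees per group for SARS-CoV and SARS-CoV-2".
- Section 4.1 requires of every participant: "Completed a 2 dose primary immunisation course against COVID-19", with the last dose at least 12 weeks earlier.
- Section 4.2 excludes those who "Have an anti-SARS-CoV-2 and a SARS-CoV-1 RBD response of more than 2 AUC (Area Under the Curve) units".

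**The concern.** The section uses one name for two endpoints that can give different counts in the same people. This population has been immunised against one of the two viruses and is being boosted, so SARS-CoV-2 RBD antibody may be present before the first dose of pEVAC-PS. A definition based on a positive readout does not separate that antibody from a response to the study vaccine.

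The antigen rule is a second gap. The only antigen wording in the section is *and/or*, so a responder may be someone whose SARS-CoV-2 antibody was boosted and who made no SARS-CoV response. Section 1.2 describes the vaccine as both boosting SARS-CoV-2 immunity and inducing SARS-CoV antibody, and Section 2 looks for both at group level.

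The count decides whether a group is expanded, whether higher-dose groups are opened, whether the trial concludes, and whether the 0.2 mg dose is taken into Phase II. The trial is open label, and Section 5.8.2 says the serology laboratory can identify the treatment group. An unresolved rule could therefore be settled after results are known.

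**Working it through.** The protocol gives no power, error rate or derived sample size for these rules, so there is no stated figure to reproduce. The check applies exact binomial tails to the protocol's own thresholds. **All response rates, baseline shares and assay SDs below are assumptions**; the documents give none.

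**Formula.** For n participants with per-person responder probability p, P(X ≥ k) = Σ C(n,j) p^j (1−p)^(n−j), summed over j = k to n.

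**1. Literal definition (positive readout, either antigen), no vaccine effect.** Here p is the share already SARS-CoV-2 RBD-positive on Day 0.

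| Baseline-positive share | P(≥5/6) | P(≥10/12) | P(≥7/9) |
|---|---|---|---|
| 0.8 | 0.655 | 0.558 | 0.738 |
| 0.9 | 0.886 | 0.889 | 0.947 |
| 0.95 | 0.967 | 0.980 | 0.992 |
| 1.0 | 1.000 | 1.000 | 1.000 |

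The Section 4.2 exclusion does not clearly limit this share. As worded, with *and*, it removes only people above 2 AUC units on both antigens. Someone high on SARS-CoV-2 and low on SARS-CoV-1 can enrol.

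**2. The 2-fold branches, no vaccine effect.** With SD s for a single log2 titre, the chance of an apparent 2-fold rise on one antigen is q = 1 − Φ(1/(s√2)), and on either of two independent antigens u = 1 − (1−q)².

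- s = 0.7: q = 0.156, u = 0.288, P(≥5/6) = 0.009.
- s = 1.0: q = 0.240, u = 0.422, P(≥5/6) = 0.052.

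So if the 2-fold rule operates, static baseline antibody plus assay noise rarely meets the Stage 1 target.

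**3. The 2-fold branches with a real response.** Let a and b be the SARS-CoV-2 and SARS-CoV response rates. With independent responses, *either* gives p = 1 − (1−a)(1−b) and *both* gives p = ab.

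| a | b | P(≥5/6), either | P(≥5/6), both |
|---|---|---|---|
| 0.9 | 0 | 0.886 | 0 |
| 0.8 | 0.2 | 0.753 | 0.0005 |
| 0.8 | 0.5 | 0.886 | 0.041 |
| 0.8 | 0.5 (fully nested) | 0.655 | 0.109 |

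First row in full: 6 × 0.9⁵ × 0.1 + 0.9⁶ = 0.3543 + 0.5314 = 0.886. With b = 0 this row needs no independence assumption. At 10 of 12 the same rates give 0.889 under *either* and 0 under *both*.

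**4. Effect of the antigen rule on the Stage 1 branches.** Take a = b = 0.5, independent, so p is 0.5 for one named antigen, 0.75 for *either* and 0.25 for *both*.

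| Rule | ≥5/6 | 3–4/6 | ≤2/6 |
|---|---|---|---|
| One named antigen | 0.109 | 0.547 | 0.344 |
| Either | 0.534 | 0.428 | 0.038 |
| Both | 0.005 | 0.165 | 0.831 |

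Positive correlation narrows these gaps. If the two responses were fully nested at equal rates, the three rows would coincide at the first.

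**The case against.** The strongest reply is that the 2-fold rise is plainly the operative rule. Every numeric branch uses it and none counts positive readouts. That stands in part. A reader might infer that the target is almost certain to be met on Day 0 with no vaccine effect. That follows only if the stated thresholds are set aside in favour of the literal definition, and step 2 shows the 2-fold rule does not behave that way. It does not remove the contradiction, because the section says decisions rest on seroconversion and defines that differently. Nor does it supply an antigen.

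A reader might also infer that Section 2 requires each participant to respond to both antigens. It does not. It describes responses in the majority of vaccinees per group, which most naturally means a majority for each antigen. A per-person rule requiring both would be stricter than Section 2.

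Nor is it a contradiction that eligibility is expressed in AUC units and the decision rule in titre. They serve different purposes and need not match.

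The last reply is that Section 8.1 lets investigators use all available tolerability and immunogenicity information, and Section 8.2 reports geometric mean fold changes at each time point, so an absent SARS-CoV response should be visible. Boosting SARS-CoV-2 immunity is also a stated aim. All this is true, but visibility in the data does not say how a SARS-CoV-2-only result is to be classed under a rule fixed in advance.

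**Conclusion.** The point holds as an internal inconsistency in a rule that the protocol itself fixes, so it is not detail that can be left to the SAP. Section 3.1.1 has two non-identical responder definitions and no resolved antigen rule.

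On the literal definition, antibody already present on Day 0 can count. On the more charitable reading, where only the 2-fold branches operate, a rise is needed but a SARS-CoV-2-only boost still meets the Stage 1 target, with probability 0.886 at assumed rates of 0.9 and 0. That figure illustrates what the rule permits and does not predict the outcome. The independent two-antigen contrasts in steps 3 and 4 are towards the wide end, since a single RBD antigen is meant to drive both responses and positive correlation is likely.

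**What to change.** Reconcile the text of Section 3.1.1 and carry the result into the SAP:

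1. Remove the positive-readout definition.
2. Use one responder definition at all stages: a 2-fold or greater rise from the participant's own Day 0 value to the value 28 days after dose 2, in one stated ELISA measure.
3. Replace *and/or* with an explicit antigen rule, chosen by the sponsor and consistent with Section 2. One example is counts per antigen with SARS-CoV named as required.
4. Report antigen-specific counts at each review.
5. Recheck the existing count thresholds against the chosen definition. Step 4 of the working shows why: at 0.5 per antigen and independence, moving from one named antigen to both raises the chance of the 2-or-fewer branch from 34% to 83%. The antigen rule therefore affects escalation and cannot be treated as wording alone.

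The cost is a protocol and SAP amendment plus the threshold check. Immunology blood is already scheduled on Day 0 and Day 56, so no new samples or assays are needed. The downside is that, if a SARS-CoV response is required, the target is harder to meet than under an either-antigen rule.
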